5.5.3. Supportive Secondary Endpoint(s)

To understand and characterize the vaccine efficacy against any symptomatic infection, as well as under any infection, the following supportive endpoints will be supplemented with the confirmatory secondary endpoints.

The evaluation of secondary endpoints will be done in the per-protocol analysis set in seronegative subjects, with onset at least 14 and at least 28 days after double-blind vaccination. All analyses will be repeated regardless of serostatus.

	Endpoint definition
Mild infection	A subject is considered as an event when the first occurrence of molecularly confirmed COVID-19 case meeting mild definition with onset at least 14 and at least 28 days post double-blind vaccination.
Moderate infection	A subject is considered as an event when the first occurrence of molecularly confirmed COVID-19 case meeting moderate definition with onset at least 14 and at least 28 days post double-blind vaccination.
US FDA Harmonized COVID-19 cases	A subject is considered as an event when the first occurrence of molecularly confirmed COVID-19 case meeting the US FDA harmonized case definition with onset at least 14 and at least 28 days post double-blind vaccination
Viral Load AUC (VL-AUC)	
Area under the viral load-time curve (VL-AUC in \log_{10} copies/ml) of SARS-CoV-2 viral RNA load as determined by quantitative RT-PCR assay of nasal available samples during the COVID-19 episode.
 
Nasal swab samples are taken at the start of the COVID-19 episode and every 2 days thereafter for the next 14 days or until 2 consecutive negative swabs, whichever occurs later.
 
VL-AUC is calculated based on the viral load values until resolution of the COVID-19 episode.
 
In the calculation of the AUC, all available information (date, timing in hours, and minutes as captured in the data base will be used, but the AUC result will be reported in hours), of the assessment, is taken into account.
 
Data handling regarding the following will be added to the Data Presentation Specifications (DPS):
 
 • PCR local lab versus central lab data • saliva • handling of values below LLOQ/LLOD

	$AUC VL = \sum_{i=2}^T \frac{[VL_{t_i} + VL_{t_{(i-1)}}]}{2} [t_i - t_{(i-1)}]$ 
where
 
t_i = (actual) timepoint i
 
t_{i-1} = (actual) timepoint $(i-1)$
 
T = last timepoint
 
t_1 = first timepoint
 
VL_{t_i} = \log_{10} viral load at (actual) timepoint i
 
$VL_{t_{(i-1)}}$ = \log_{10} viral load at (actual) timepoint $(i-1)$
 
This will be calculated for all subjects with a molecularly confirmed infection.

--	---

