The trial will enroll and randomize large numbers of adult participants in different populations. Until 1 year after the Month 6/unblinding visit, each participant will be asked at least twice a week, through the electronic clinical outcome assessment (eCOA), if they have experienced any new symptoms or health concerns that could be related to infection with SARS-CoV-2. As of 1 year after the Month 6/unblinding visit, until the end of the long-term follow-up period, the frequency of this surveillance question through the eCOA will decrease to once every 2 weeks. Vaccine efficacy to prevent mild COVID-19, to prevent COVID-19 of any severity (burden of disease), to prevent acquisition of asymptomatic SARS-CoV-2 infection, to prevent COVID-19 requiring medical intervention, to prevent acquisition of any SARS-CoV-2 infection and to investigate SARS-CoV-2 viral load for moderate to severe/critical COVID-19 cases are secondary objectives. The design has continuous monitoring of events to report results upon early evidence of vaccine efficacy, lack of efficacy, or vaccine safety concerns. The trial is powered to provide sufficient evidence of safety and vaccine efficacy to prevent COVID-19 in support of possible (potential) marketing authorizations. Note that in Protocol Amendment 3, the sample size was reduced from 60,000 to approximately 40,000 participants.

The study will have the following timepoints for efficacy analyses:

1. The evaluation of the primary objective will be performed as soon as the target number of events (TNE) has been reached in the double-blind phase for both co-primary endpoints, or earlier based on sequential monitoring of both co-primary endpoints. Sponsor unblinding will occur but investigator and participants remain blinded until implementation of CTPA4.
2. If an efficacy signal is triggered before the required 8-week follow-up after double-blind vaccination of 50% of participants is reached, an additional analysis will be performed when that follow-up timepoint is reached (8-week median follow-up timepoint). If the time between the efficacy signal and the required 8-week median follow-up is too short to make a difference in terms of preparing two analyses then a single analysis will take place at the time of the 8-week median follow-up. The analysis at the time of the 8-week median follow-up is considered the primary analysis.

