To assess the effect of Ad26.COV2.S on COVID-19 requiring medical intervention (based on objective criteria) compared to placebo	
 First occurrence of COVID-19 requiring medical intervention (such as a composite endpoint of hospitalization, intensive care unit [ICU] admission, mechanical ventilation, and extracorporeal membrane oxygenation [ECMO], linked to objective measures such as decreased oxygenation, X-ray or computed tomographic [CT] findings) and linked to any molecularly confirmed^a, COVID-19^{b,c} at least 14 days after double-blind vaccination (Day 15) First occurrence of COVID-19 requiring medical intervention and linked to any molecularly confirmed^a, COVID-19^{b,c} at least 28 days after double-blind vaccination (Day 29)
To assess the effect of Ad26.COV2.S on SARS-CoV-2 viral ribonucleic acid (RNA) load compared to placebo for moderate to severe/critical COVID-19 ^b	Assessment of the SARS-CoV-2 viral load by quantitative reverse-transcriptase polymerase chain reaction (RT-PCR), in participants with molecularly confirmed ^a , moderate to severe/critical COVID-19 ^b by serial viral load measurements during the course of a COVID-19 episode
To assess the effect of Ad26.COV2.S on molecularly confirmed ^a mild COVID-19 ^c	
 First occurrence of molecularly confirmed^a, mild COVID-19^b, at least 14 days after double-blind vaccination (Day 15) First occurrence of molecularly confirmed^a, mild COVID-19^b, at least 28 days after double-blind vaccination (Day 29)
To assess the effect of Ad26.COV2.S on COVID-19 as defined by the United States (US) Food and Drug Administration (FDA) harmonized case definition ^d	
 First occurrence of molecularly confirmed^a COVID-19^b at least 14 days after double-blind vaccination (Day 15) First occurrence of molecularly confirmed^a COVID-19^b at least 28 days after double-blind vaccination (Day 29)

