5.5.4.5. AUC viral load

To compare VL-AUC after infection between the active and placebo groups, the exact Wilcoxon Rank Sum test will be performed.

Values below the LLOQ will be imputed with 1 when detected and with 0 when not detected.

These imputations will be used when calculating the AUC based on equation (1). In addition, in case some observations are missing at the first timepoint after infection and/ or the last timepoint after challenge, missing values should be imputed with 0. No other missing values will be imputed.

AUC-VL values will be descriptively summarized (mean, median, SD, SE, range) by randomized group and COVID-19 severity (all symptomatic infections, mild, moderate to severe/critical).

Individual profiles of viral load over time and $\log_{10}[\text{viral load}]$ over time since onset of a COVID-19 episode will be summarized by randomized group and severity of COVID-19.

The vaccine efficacy against AUC-VL will be estimated through the geometric mean ratio of AUC-VL with associated 95% confidence interval.

As the comparison of the AUC VL after infection between the active and placebo groups is based on post-randomization groups, this analysis may not assess the causal effect of the vaccine on viral load. A sensitivity analysis as described by Gilbert et al. (2003) will be carried out. In this sensitivity analysis, a logistic selection bias model is employed to define a causal estimator for the vaccine effect on viral load. The unknown slope (b) of this logistic model determines the amount of selection bias; b is varied over a plausible range of values. For each value of b , a non-parametric estimate of the causal vaccine effect is calculated. A confidence interval and p-values for the appropriate hypothesis of interest are obtained by bootstrap. If $b < 0$, there is a selection bias towards a lower viral load in the vaccine group as compared to the placebo group. When $b = 0$, no selection bias is assumed. The hypothesis of interest is the one-sided hypothesis of a reduction of the viral load. Therefore, values of $b \leq 0$ will be considered (from -5 to 0 in steps of 0.01). The estimate of the causal vaccine effect with its $100*(1-2*\alpha)$ % confidence interval and the p-value for the one-sided hypothesis of a viral load reduction in the vaccine group will be plotted against the assumed value of b .

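### The secondary viral-load test is not limited to the moderate to severe/critical cases that its objective names

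*SAP*

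**What the plan says.** The objective appears twice with the same population. The introduction lists, among other aims, "to investigate SARS-CoV-2 viral load for moderate to severe/critical COVID-19 cases are secondary objectives". The table in section 1.1 words it as "To assess the effect of Ad26.COV2.S on SARS-CoV-2 viral ribonucleic acid (RNA) load compared to placebo for moderate to severe/critical COVID-19", and the matching endpoint is serial viral load in those same cases.

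Section 5.5.3 defines the AUC from nasal samples taken during a COVID-19 episode, up to its resolution, and closes the definition with: "This will be calculated for all subjects with a molecularly confirmed infection".

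Section 5.5.4.5 gives the analysis:

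- Test: "To compare VL-AUC after infection between the active and placebo groups, the exact Wilcoxon Rank Sum test will be performed".
- Estimate: "The vaccine efficacy against AUC-VL will be estimated through the geometric mean ratio of AUC-VL with associated 95% confidence interval".
- Descriptive summaries are broken down "by randomized group and COVID-19 severity (all symptomatic infections, mild, moderate to severe/critical"), and individual profiles are also shown by severity.
- The section warns that, because the groups are formed after randomization, "this analysis may not assess the causal effect of the vaccine on viral load". It adds a logistic selection-bias sensitivity analysis with slope b from -5 to 0.

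Neither the test, nor the ratio, nor the sensitivity analysis carries a severity restriction. Section 5.6.1.2 repeats the method for mild cases alone and gives the viral load of asymptomatic cases at the unblinding visit its own Wilcoxon comparison.

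**The concern.** Three statements that should describe one population do not. The objective is about moderate to severe/critical disease, the variable is derived for every confirmed infection, and the comparison is made between arms with no restriction. A programmer who follows 5.5.3 and 5.5.4.5 will put at least the mild cases into the secondary test. The p-value and ratio would then describe a different group from the one named in the objective, and no test or ratio is specified for the named group.

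A second question is bias. The planning assumptions give the vaccine higher efficacy against more severe disease, so vaccine-arm cases should be milder on average. If AUC rises with severity, a pooled comparison could favour the vaccine with no effect within any severity level. Whether that matters depends on who is pooled.

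**Working it through.** The SAP gives no sample size, power, sidedness or alpha level for this comparison, so there is no stated figure to reproduce. The population conflict is settled by reading the sections side by side; the arithmetic below addresses only the size of the case-mix effect.

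**Inputs from the SAP**

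- Placebo case mix (3.5.3): 45% asymptomatic, 55% symptomatic; of the symptomatic, 20% mild and 80% moderate or severe.
- Planning VE (Table 4): 70% moderate/severe, 60% mild, 30% to 50% asymptomatic.
- Target number of moderate to severe/critical events (3.1): 154.

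**Case mix by arm, asymptomatic VE 30%**

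Placebo shares of all infections:
- moderate/severe 0.55 × 0.8 = 0.44
- mild 0.55 × 0.2 = 0.11
- asymptomatic 0.45

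Vaccine, each multiplied by (1 - VE):
- moderate/severe 0.44 × 0.3 = 0.132
- mild 0.11 × 0.4 = 0.044
- asymptomatic 0.45 × 0.7 = 0.315
- total 0.491

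Moderate/severe share:
- symptomatic cases only: placebo 0.44/0.55 = 80%; vaccine 0.132/0.176 = 75%
- all infections: placebo 44.0%; vaccine 0.132/0.491 = 26.9%

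**Counts.** With 154 moderate/severe events, placebo has 154/1.3, about 118, and vaccine about 36. Mild cases are then about 30 and 12.

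**Simulated false-positive rate.** The test is a two-sided 5% Wilcoxon (normal approximation), with 2,000 trials per setting and no vaccine effect within any level. Assumptions not in the SAP: AUC normal with SD 1 within level; a step of 0.25, 0.5 or 1.0 SD between asymptomatic, mild and moderate/severe; the share of asymptomatic infections that PCR detects and that enter the test; the 5% level. Counts per level are fixed at their rounded expected values.

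| Who enters the test | Step 0.25 SD | 0.5 SD | 1.0 SD |
|---|---|---|---|
| Symptomatic only | 4.8% | 4.7% | 4.5% |
| Plus 10% of asymptomatic (VE 30%) | 5.7% | 6.8% | 8.8% |
| Plus 25% of asymptomatic (VE 30%) | 6.8% | 12.1% | 25.5% |
| Plus all asymptomatic (VE 30%) | 12.7% | 32.0% | 79.3% |
| Plus all asymptomatic (VE 50%) | 7.0% | 10.9% | 24.0% |

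A second run of the symptomatic-only setting gave 4.4%, 6.0% and 3.8%. Simulation error at 5% is about 1.96 × sqrt(0.05 × 0.95/2000) = 1 percentage point, so neither run shows clear inflation.

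Because fixed counts can hide a small shift, here is a direct check at the largest step. The difference in means from case mix is (0.80 - 0.75) × 1.0 = 0.05 SD. With 148 and 48 cases the standard error is about sqrt(1/148 + 1/48) = 0.166 SD. The shift is 0.05/0.166 = 0.30 standard errors, so a two-sided 5% test rejects with probability of about P(Z > 1.66) + P(Z < -2.26) = 0.048 + 0.012 = 6%. That is still negligible.

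**After restriction** to moderate to severe/critical cases (118 against 36), 4,000 simulated trials rejected in 4.4%. Moderate and severe/critical were treated as one level, so a shift between those two is not covered.

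**The case against.** The best case against the point is that the intention is clear enough. The objectives table fixes the population. The mild-only repeat in 5.6.1.2 makes most sense if the main analysis is already the moderate to severe/critical one. AUC has to be derived beyond those cases to fill the severity summaries, so the 5.5.3 sentence is not wrong in itself. The endpoint is supportive and outside the key confirmatory list, and 5.5.4.5 openly discloses the post-randomization problem.

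Much of this stands: it limits the weight of the point and shows that the fault lies in 5.5.4.5 more than in the derivation. It does not remove the conflict. Section 5.6.1.2 shows that the authors write a severity restriction when they want one, and none is written for the secondary test. The sensitivity analysis names no severity set either, and the summaries by severity are descriptive.

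A reader might go further and infer that asymptomatic positives with a single swab enter the test with an AUC of zero, since the AUC sum starts at the second sample, and so produce a spurious vaccine effect. On that reading, with 300 placebo and 100 vaccine infections and 2%, 5% or 10% of placebo infections single-swab, a one-sided 2.5% test rejects in about 4%, 9% and 21% of null trials. The SAP does not support it:

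- 5.5.3 ties the AUC to an episode, and 5.2.2 defines an episode by the onset of symptoms.
- The widest category in 5.5.4.5 is all symptomatic infections.
- 5.6.1.2 analyses asymptomatic viral load separately.
- 5.5.4.5 imputes 0 for a missing first or last timepoint, so a lone positive swab need not give a zero AUC where that rule applies.

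Only the literal wording of the one sentence in 5.5.3 leaves the door open.

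**Conclusion.** The point holds as a mismatch of population. As written, the secondary Wilcoxon test, geometric mean ratio and selection-bias analysis pool milder cases and do not answer the objective in sections 1 and 1.1.

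A material case-mix bias is not shown for the population that the surrounding text describes. With symptomatic cases only and VE of 70% and 60%, the moderate/severe share differs by 5 percentage points and the false-positive rate stays close to nominal. Inflation appears only if PCR-detected asymptomatic infections are pooled. It then ranges from slight to severe, depending on the detected share, the asymptomatic VE and the severity step. The detected share and the step are assumptions, not SAP figures.

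**What to change.** In 5.5.4.5, state that the Wilcoxon test, the geometric mean ratio and the selection-bias sensitivity analysis for the secondary objective use molecularly confirmed moderate to severe/critical episodes. In 5.5.3, state that AUC is calculated for all symptomatic cases, to serve the severity summaries, and that asymptomatic PCR positives without an episode get no AUC. Leave the mild and asymptomatic analyses exploratory, as 5.6.1.2 has them. Do not add a minimum number of swabs as an entry condition: that would be a further exclusion made after randomization, and it is not needed.

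The change is wording only and needs no new data. The cost is fewer cases in the test: in the illustration, 118 and 36 in place of 148 and 48. The restricted comparison still conditions on an outcome that the vaccine affects, so the sensitivity analysis must stay, run on the same cases. Section 1 says that sponsor personnel were unblinded at the primary analysis, so the amendment should be recorded as bringing the analysis into line with the objective already written, not as a fresh choice of population.

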5.5.4. Analysis Methods for double blind phase

5.5.4.1. VE against severe/critical infection with onset at least 14 and at least 28 days after double-blind vaccination

The VE will be estimated with an associated two-sided (1-2 α^*) confidence interval (methodology described in Appendix 8). The alpha-level α^* is derived as detailed in section 2. To evaluate the hypothesis $H_0: VE \leq 0\%$, the lower-limit of the adjusted confidence interval will be compared to 0, the hypothesis of moderate to severe infection with onset at least 14 and at least 28 days after double-blind vaccination will be rejected if the lower limit of the confidence interval is $> 0\%$.

A descriptive summary of the reason for severe disease, as indicated by the adjudicators will be provided.

To assess potential time-effects of VE, two additional graphical explorations will be conducted. First, the Kaplan-Meier method will be used to plot the estimated cumulative incidence rates over time for the vaccine and placebo groups. This method will be used to estimate cumulative VE over time, defined as $[(1 \text{ minus ratio (vaccine/placebo)} \text{ of cumulative incidence by time } t) \times 100\%]$ with the method of Parzen, Wei and Ying applied to estimate pointwise and simultaneous $(1 - \alpha) \times 100\%$ CIs. Secondly, the method of Gilbert et al. (2002) will be used to evaluate VE over time based on the ratio of the smoothed instantaneous hazard in the vaccine and the placebo arm. More specifically, graphs will be created with $[(1 \text{ minus ratio (vaccine/placebo)} \text{ of smoothed instantaneous hazard by time } t) \times 100\%]$ and accompanying pointwise and simultaneous $(1 - \alpha) \times 100\%$ CIs over time since vaccination.

Vaccine efficacy will be summarized for the following time intervals, Day 1-14, Day 15-28, Day 29-56, Day 57-end DB phase. The interval Day 56-end of double blind may be further separated into Day 56-112 and Day 112-End of double blind phase, whereby Day 56 and Day 112 correspond to approximately median F/U times of the primary and final analysis of the double blind phase respectively.

5.5.4.2. VE against any symptomatic infection – burden of disease

To evaluate the vaccine efficacy against any symptomatic infection, the severity-adjusted vaccine efficacy VE_{BOD} will be calculated based on BOD as follows. This vaccine efficacy measure is equal to the percent reduction in mean BOD score in the vaccine arm relative to that in the placebo arm.

Letting p_1 and p_2 denote, respectively the relative incidence of mild and moderate infections among symptomatic infections, and VE_1 , VE_2 , VE_3 represent, respectively, the vaccine efficacy for mild, moderate and severe/critical infections, the vaccine efficacy for BOD, under 1:1 allocation for vaccine and placebo, can be expressed as

$$VE_{BOD} = 1 - [(1 - VE_1)p_1 + (1 - VE_2)p_2 + 2(1 - VE_3)(1 - (p_1 + p_2))]/(2 - (p_1 + p_2))$$

Letting $BOD_V(n)$ and $BOD_P(n)$ represent the sums of the BOD scores for (symptomatic) infections in the vaccinated and placebo arms, respectively, then the estimated vaccine efficacy for the BOD endpoint after n infections (under equal allocation to vaccine and placebo) is $\widehat{VE}_{BOD}(n) = 1 - BOD_V(n)/BOD_P(n)$. An expression for an (asymptotic) lower confidence bound for VE_{BOD} based on $\widehat{VE}_{BOD}(n)$ is provided in (supplementary appendix, Mehrotra et al, 2020). The alpha* - level of the confidence interval will be compared against 0.

This lower bound will be compared against 0% to evaluate the study hypothesis against any symptomatic infection according to the statistical testing strategy specified in section 2.

In addition, the vaccine efficacy will be estimated with an associated unadjusted confidence interval for each severity separately (mild, moderate, severe/critical) according to the case definition.

Estimators for VE_1 , VE_2 and VE_3 in the PP-SN, together with their 95% CIs, are presented in Appendix 8.

In addition, to assess potential time-effects of VE, the Kaplan-Meier method will be used to plot the estimated cumulative incidence rates over time for the vaccine and placebo groups. This method will be used to estimate cumulative VE over time, defined as $[(1 - \text{ratio (vaccine/placebo) of cumulative incidence by time } t) \times 100\%]$ with the method of Parzen, Wei and Ying applied to estimate pointwise and simultaneous $(1 - \alpha) \times 100\%$ CIs.

Vaccine efficacy for any symptomatic COVID-19 will be summarized for the following time intervals, Day 1-14, Day 15-28, Day 28-56, Day 56-end DB phase. The interval Day 56-end of double blind may be further separated into Day 56-112 and Day 112-End of double blind phase, whereby Day 56 and Day 112 correspond to approximately median F/U times of the primary and final analysis of the double blind phase respectively.

5.5.4.3. Any SARS-CoV-2 infections and asymptomatic infections

The proportion of subjects (out of subjects with available measurements) who serologically converted will be graphically visualized and tabulated at every available timepoint by randomized group, together with the number of subjects with an available measurement.

Additional tabulation will summarize the number of subjects with and without a SARS-CoV-2 infection as having

1. Not infected
2. Asymptomatic infections
 - Based on serological conversion
 - Based on positive RT-PCR
3. Symptomatic molecularly confirmed, with mild COVID-19
4. Symptomatic molecularly confirmed, with moderate COVID-19
5. Symptomatic molecularly confirmed, with severe COVID-19
6. Symptomatic serologically confirmed, with mild COVID-19
7. Symptomatic serologically confirmed, with moderate COVID-19
8. Symptomatic serologically confirmed, with severe COVID-19

A subject will be classified based on their worst occurrence and in one category only.

All subjects with multiple SARS-CoV-2 molecularly confirmed infections during the study will be tabulated by severity and double-blind vaccination group in the FAS-SN as well as SP set.

To assess the effect of Ad26.COV2.S on occurrence of any infection with SARS-CoV-2 as compared to placebo, VE will be estimated with an associated 95% confidence interval. If the timepoint of hypothesis testing is reached (when at least 15,000 subjects with a Day 71 available sample), adjusted two-sided (1- $2\alpha^*$) confidence interval (methodology described in Appendix 8). The alpha-level α^* is derived as detailed in section 2. To evaluate the hypothesis $H_0: VE \leq 0$, the

lower-limit of the adjusted confidence interval will be compared to 0, the hypothesis of protection against infection will be rejected.

To understand the vaccine efficacy of Ad26.COV2.S on occurrence of asymptomatic infections with SARS-CoV-2 alone, as compared to placebo, the VE will be estimated with a 95% confidence interval. If the timepoint of confirmatory testing is reached (when all participants have at least 6 months of follow-up), an associated adjusted two-sided (1- $2\alpha^*$) confidence interval (methodology described in Appendix 8). The alpha-level α^* is derived as detailed in section 2. To evaluate the hypothesis $H_0: VE \leq 0$, the lower-limit of the adjusted confidence interval will be compared to 0, the hypothesis of protection against infection will be rejected.

For cases, the follow-up time is defined as the time between double-blind vaccination and the time of onset of infection (timepoint of a positive N-protein Elisa for asymptomatic subjects).

For supportive endpoints, Vaccine efficacy will be estimated with a 95% confidence intervals (as described in appendix 8).

